Participant Eligibility: Postpartum women 15-49 years presenting with their infants to the CYC or PCAC for a 2-month WBV, and who also receive their own care at UIC (needed for chart abstraction purposes), are eligible to participate in the study. Women must be English and Spanish speakers.

Participant Exclusion: Women who are currently pregnant, less than 15 years or older than 49 years of age, or do not speak English or Spanish.

Participant Recruitment into the Research Study: The intervention is planned as a system-level intervention, thus, all women whose infants are scheduled for a 2-month WBV during the intervention period will have the opportunity to be exposed to the RLPT intervention. On study recruitment days (randomly selected half-days during phase 2), women whose infants are scheduled for a 2-month WBV will be approached by a

research assistant (RA) who will screen for eligibility. Recruitment into the study will occur before, during or after the WBV, baseline surveys will be completed during or after the WBV to avoid biasing women's responses on the RLPT, which is administered *prior* to the WBV. If a woman is eligible and interested in participating, she will be consented and asked if she has time to complete a baseline survey. The baseline survey will include the domains listed in Table 1. To the extent possible, the baseline survey will be self-administered using a tablet computer linked to the RedCap database. A study RA will be available to provide assistance or administer the survey if necessary. When possible, the surveys will be completed immediately after the WBV in a private room. We are sensitive to the fact that women may not have the time to stay after the WBV, in which case we will request permission to conduct the survey by phone at a convenient time. Our research team has extensive experience recruiting PP participants and we have found this to be an effective strategy. Because this is a system-level intervention, women who decline participation in the study will still receive the intervention but will not participate in any research data collection. For example, a woman who does not agree to participate in the study would still have been given the RLPT prior to the infant's visit and, if desired, she will receive a referral and appointment for care though she will not be included in the study.

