Clinical Operations Visit time and day of week	II	Health System	Enrollment	Medical record schedule	Covariate
Health and Family Planning					
Women’s general health status	I	Women	Enrollment	Baseline Survey	Covariate

Women's general health behaviors (smoking, alcohol, nutrition and exercise)	I	Women	Enrollment	Baseline Survey	Covariate
Plans for future pregnancy	I	Women	Enrollment	RLPT	Covariate
Current contraception type and use	I	Women	Enrollment	RLPT	Covariate
Pregnancy status	I	Women	6 months postpartum	Phone survey and Chart review	Dependent
Referral to primary care	I	Women	Enrollment	RLPT	Dependent
Receipt of primary care visit	I	Women	6 months postpartum	Phone survey and Chart review	Dependent
Use contraception, duration and method	I	Women	6 months postpartum	Phone survey and Chart review	Dependent
Feasibility, Acceptability, and Adoption of RLPT					
Ease of use, comfort and satisfaction with tool	II	Physician	Year 2	Focus groups	Acceptability
Ease of use, comfort and satisfaction with tool	II	Women	Enrollment	Baseline survey	Acceptability
Women's need and desire for referral	I and II	Women	Enrollment	RLPT	Acceptability
Women's barriers and facilitators	II	Women	6 months postpartum	Phone survey and Chart review	Feasibility
Physician barriers and facilitators	II	Physician	Completion of study	Focus groups	Feasibility
Completion rate for grey box on RLPT form	II	Health System	Enrollment	RLPT completion rate by women and physicians	Adoption

Data Sources and Collection

Surveys of Women: All participants will complete a baseline survey (English and Spanish) at the time of enrollment in the study (during or after the WBV) and will receive

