a phone call at 6 months PP for the follow-up survey (survey and interview questions domains listed in Table 1). During the baseline survey, in addition to demographic information, women will be asked about their general health status and health behaviors, and current contraception type and use. Those in intervention arm will be asked about their experience completing the RLPT during the WBV, referral to well-woman primary care (if applicable). For the follow-up survey we will try to reach each participant as close to 6 months as possible, but no later than 9 months PP. Structured phone interviews with women will include questions from the following domains: 1) use of health care services; 2) use and type(s) of contraception; and 3) known pregnancy status. The intervention group interviews will also include experience completing the RLPT during the WBV; and, the process of getting care (for those who chose to do so) (SA II). To verify RLPT exposure at the individual level, the RLPT tool will be linked to the mother using the patient sticker placed on the tool.

Medical Records: Medical records will be reviewed at baseline and at 6 months PP to determine receipt of health care services and contraception. We recognize that some women may receive additional health care outside the UIC system; for this group, we will not be able to confirm medical visits outside the UIC system.

Focus Groups with Providers: We will conduct two in-depth qualitative focus groups with physicians (residents and faculty) after the intervention is complete during study year 2. The focus group guide will include questions from the following domains: 1) Experience implementing the RLPT; and, 2) barriers and facilitators to implementation of RLPT (SA II). In addition, study investigators will keep a running log of barriers and facilitators experienced throughout the intervention implementation period.

Data Management

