All survey data will be directly entered into REDcap web-based data capture screens that will be programmed and tested prior to the study. Data will be imported to SAS for analysis. Variables (Table 1) will be merged across time point by study ID and cleaned and recoded. Focus groups will be recorded, transcribed, and uploaded to DeDoose qualitative analysis software. Completion of the Grey Box (physician section of the tool) will be a measure of provider “adoption” of the intervention; completion rates will be tracked by comparing completed forms with completed clinic visits for 2-month WBVs. Completed clinic visit data are available in our existing medical record scheduling system.

Analysis

Specific Aim I and Ia: Baseline characteristics will be assessed for equivalency across groups using chi-square tests for categorical and t-tests for continuous variables. Unbalanced characteristics will be adjusted for in further analyses. The primary outcome, receipt of primary care services for women by 6 months PP (SA I) will be ascertained both by self-report during the 6-month phone interview and by medical record review, in order to minimize missing data. Evidence of a visit from either source

will be counted as receipt. Utilization, type and duration of contraception (SA 1a) by 6 months PP will be assessed similarly. An intent-to-treat analysis will be performed for SA I and 1a. A crude relative risk (RR) and risk difference (RD) will be calculated with 95% confidence intervals to estimate the effect of the intervention on primary outcomes. If adjustment is needed for covariates, RRs and RDs will be estimated using the average marginal predictions from a fitted logistic regression model with the following form:⁴¹

$$\text{logit}(y) = \beta_0 + \beta_1x_1 + \beta_2x_2 + \dots + \beta_kx_k, \text{ where:}$$

y =	SA 1: Woman's primary care visit by 6 months (1 = Yes/0 = No)
	SA 1a: Use of contraception at 6 months (1 = Yes/0 = No)
x ₁ =	RLPT Intervention (1 = Intervention/0 = Control)
x ₂ – x _k =	Unbalanced covariates

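### Late phone baseline surveys have no cut-off date, so in the intervention arm they can record contraception and health behaviours after exposure, which the plan may then adjust for

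*Combined protocol and SAP*

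**What the plan says.** **Timing.** Under Participant Recruitment into the Research Study, the RLPT is given before the WBV, and "baseline surveys will be completed during or after the WBV to avoid biasing women's responses on the RLPT". The preferred arrangement is prompt: "When possible, the surveys will be completed immediately after the WBV in a private room". A woman without time is offered a call, "in which case we will request permission to conduct the survey by phone at a convenient time". Surveys of Women describes the survey as done on enrolment: "All participants will complete a baseline survey (English and Spanish) at the time of enrollment in the study (during or after the WBV". The follow-up survey has an outer limit, "as close to 6 months as possible, but no later than 9 months PP"; the baseline survey has none.

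**Content.** At baseline, "women will be asked about their general health status and health behaviors, and current contraception type and use".

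**Use.** Under Analysis, Specific Aim I and Ia, groups are compared by chi-square and t-tests, with no significance level stated. Then: "Unbalanced characteristics will be adjusted for in further analyses". Crude RR and RD with 95% confidence intervals are calculated in any case.

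**Source of baseline contraception.** Table 1 lists current contraception as a covariate taken from the RLPT. Surveys of Women puts it in the baseline survey. Medical Records adds a chart review at baseline that covers contraception. Controls are enrolled in phase 1, before the RLPT is introduced, so they never complete one.

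**The concern.** In the intervention arm the order is RLPT, pediatrician's conversation, possible referral, then survey. Study Design and Intervention lets a referred woman take the next available appointment. Nothing prevents her baseline call from falling after that appointment, and a question about current use then describes her status on the day of the call. Controls follow the same survey procedure with no RLPT or RLPT-prompted referral before it.

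If contraception started because of the RLPT is recorded as baseline use and entered in the logistic model, part of the effect is treated as a pre-existing difference and removed. Aim Ia is the most exposed, because baseline use is likely to be a strong predictor of use at 6 months. The groups are sequential and not randomised, so the plan relies on this adjustment whenever they differ.

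**Working it through.** **The plan's own figures.** The documents contain no figure for this point and no power calculation. The one related calculation is recruitment: 200 × 0.57 = 114 two-month WBVs per month, and 114 × 4 months × 0.4 of half-days × 0.4 participation = 73. That supports at least 50 per group, the size used below.

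**Can the RLPT supply the contraception covariate?** It is completed before the conversation, so it would be a better-timed value. It does not exist for controls, so it cannot enter a between-group balance test or model. That leaves the survey item or the chart, and the Analysis section names neither.

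**Illustration for Aim Ia. Every rate is an assumption.**
- True use before the RLPT, both groups: b = 0.60 (range 0.50-0.70).
- Users still using at 6 months: r = 0.90.
- Non-users who are using at 6 months: q0 = 0.30 in controls, q1 = 0.60 in the intervention group.
- Share of all intervention non-users who have already started when surveyed: s.

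True RD = (1 − b)(q1 − q0) = 0.40 × 0.30 = 0.120.

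Recorded baseline use is C0 = b in controls and C1 = b + (1 − b)s in the intervention group. Intervention women still recorded as non-users have 6-month use p = (q1 − s·r)/(1 − s). Recorded users have r in both groups and contribute no difference. Standardising to the pooled share of recorded users, c = (C0 + C1)/2, gives adjusted RD = (1 − c)(p − q0).

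| s | Baseline shift | p | c | Adjusted RD | Points lost |
|---|---|---|---|---|---|
| 0.10 | 4 points | 0.51/0.90 = 0.567 | 0.62 | 0.38 × 0.267 = 0.101 | 1.9 |
| 0.20 | 8 points | 0.42/0.80 = 0.525 | 0.64 | 0.36 × 0.225 = 0.081 | 3.9 |
| 0.30 | 12 points | 0.33/0.70 = 0.471 | 0.66 | 0.34 × 0.171 = 0.058 | 6.2 |

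About half of each shift is lost. For b from 0.50 to 0.70, the adjusted RD is about 84%, 67% and 49% of the true RD at s = 0.10, 0.20 and 0.30. A large-sample simulation of the plan's method (main-effects logistic model, average marginal predictions) agreed to within about 0.002. Adjusting for true pre-RLPT use left the RD unchanged.

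**What s might be.** Only women surveyed late can contribute. If 20-40% of intervention women were surveyed late by phone and 10-25% of the non-users among them had started, s = 0.20 × 0.10 = 0.02 to 0.40 × 0.25 = 0.10. At s = 0.02, p = 0.582/0.98 = 0.594, c = 0.604 and the adjusted RD is 0.396 × 0.294 = 0.116. The lower two rows of the table therefore need more or later phone surveys than these rates imply.

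**How often the item would be flagged.** With n = 50 per group and alpha 0.05 two-sided (assumed), the chance of significance in the direction of the shift is Φ[(C1 − C0 − 1.96·SE0)/SE1], where SE0 is the pooled and SE1 the unpooled standard error. For b = 0.60 and the 8-point shift: (0.08 − 1.96 × 0.0960)/0.0957 = −1.13, giving 0.129. Over b = 0.50-0.70 the results are 5-7% (s = 0.10), 10-17% (s = 0.20) and 18-33% (s = 0.30). With no shift it is 2.5% in that direction. The opposite tail adds at most about 1 point.

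**The case against.** The strongest reply is that the plan already favours immediate surveys and treats the phone as a fallback. For a same-day survey the mechanism is hardly credible: the conversation is expected to take under 3 minutes, pediatricians are not expected to give contraceptive counselling, and smoking, alcohol, nutrition, exercise or contraception would not change between check-in and check-out. This stands, and it confines the point to late phone surveys. A reader might infer that the whole intervention arm's baseline is contaminated, or that surveys are meant to be taken at any later time. The documents support neither; they only omit a limit.

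Second, adjustment is conditional on imbalance and the crude estimates are reported regardless. This also stands. It does not dispose of the point: in a sequential comparison the adjusted estimate is the one that will be relied on when the groups differ.

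Third, Table 1 and the baseline chart review offer other sources for contraception. That is fair, and the documents do not settle that the survey value is the one to be adjusted for. But the RLPT is unavailable in controls, and the chart review has no stated cut-off at the WBV and is not named in the Analysis section.

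**Conclusion.** The point holds for late phone surveys in the intervention arm. As written, the plan allows a post-exposure value to be recorded as baseline, and the adjustment rule has no restriction that would exclude it. The resulting bias in the adjusted RR and RD is toward the null, chiefly for Aim Ia. No size has been worked out for the primary outcome in Aim I.

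The size cannot be computed from the documents. Under the assumed rates, roughly half the induced baseline shift is lost from the adjusted RD, and only when the balance test flags the item, about 5-33% of the time. These flagging rates assume the groups are otherwise alike; a genuine difference between the sequential groups could raise or lower them. The adjusted RDs are large-sample values, not averages over flagged samples of 50 per group.

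Two stronger readings are tempting. One is that every point of baseline shift removes a point of effect; the arithmetic shows about half. The other is that the trial's effect estimate is biased as such; the crude RR and RD do not use these covariates and are untouched by this mechanism. The conflict over the contraception source stands regardless of any assumed rate.

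**What to change.** Keep the survey after the WBV, which preserves the stated reason for the order. Then:

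1. Word the covariate items in both arms to ask about status before the 2-month WBV.
2. Record the survey date and set a maximum interval from WBV to survey, with the survey done before any referred appointment. The documents give no basis for a particular length, so the sponsor should choose it.
3. Name one baseline contraception source available in both arms, either the survey item anchored before the WBV or the chart up to the WBV date, and reconcile Table 1 with Surveys of Women and Medical Records.
4. In the Analysis section, restrict adjustment to values that predate the RLPT (in controls, that predate the WBV).

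The cost is a few reworded items, a date field and a sentence in the analysis plan. Some late surveys will lose covariates, and anchored items carry some recall error. The change is best made before enrolment, because late surveys collected without a date cannot be identified afterwards.

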assess women's need for well-woman primary care, then refer and provide an appointment for care for women who desire one.

Specific Aims

Aim I. To determine if introducing a self-administered Reproductive Life Planning Tool (RLPT) with postpartum mothers during the 2-month WBV will increase the proportion of women receiving a well-woman primary care health visit by 6 months postpartum.

Aim Ia. To determine if introducing a self-administered Reproductive Life Planning Tool (RLPT) with postpartum mothers during the 2-month WBV will increase utilization rates of contraception by 6 months postpartum.

Aim II: To assess the extent of system adoption as well as patient-, provider-, and systems-level barriers and facilitators to integrating a self-administered Reproductive Life Planning Tool designed to facilitate referral of postpartum women for primary well-woman care within the context of a pediatric clinic.

Study Design and Intervention

This is a single-site system-level pilot study to measure the impact of a self-administered RLPT (attachment) during the 2-month WBV on PP women's subsequent receipt of primary health care and contraception, compared to usual care. To facilitate women's uptake of a referral for well-woman primary care, women will be offered the opportunity to schedule a visit for herself on the same day as her infant's next WBV or the first available visit if she needs more immediate care. This study will have two phases: **phase 1** is enrollment of a control or baseline group, followed by a washout period; **phase 2** is enrollment of the intervention group (intervention).

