During phase 2 (intervention), the self-administered RLPT will be implemented in the Child and Youth Center (CYC, the general pediatric clinic) and the Primary Care Adolescent and Child Clinic (PCAC) at UIH with all PP women bringing infants for the 2-month WBV. The intervention leverages an existing system designed to screen all PP women (through 6-months) for depression. Currently, when a mother checks-in her infant for a visit she is provided an Edinburgh Postpartum Depression Screening tool with instructions to complete and return the tool to the infant's physician during the visit. On a daily basis, completed tools are scanned and saved on a secure server (required for billing purposes). This system has been successful for universal PP depression screening and referral. An audit found that in 91% of all WBVs with a child 0-16 wks., the infant's mother was present and eligible to have an Edinburgh tool completed; of these, 90% had a completed Edinburgh tool provided to the physician. We will pair the RLPT with the Edinburgh tool (back to back on the same piece of paper); women of 2-month olds will be instructed to complete both sides. To test the feasibility of this approach, we briefly tested locating a general women's health screening survey on the back of the Edinburgh tool. During the pilot, 37 infants 0-16 wks. of age had a WBV; 89% of these had a complete Edinburgh. Of those who completed the Edinburgh, 100%

completed the survey on the opposite side, suggesting women are willing to complete another brief questionnaire.

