During the WBV, physicians will review the information provided by the woman on the RLPT about general health, reproductive plans, and use of contraception. The pediatrician will use the RLPT to initiate a brief conversation with mothers about the need for a referral for well-woman primary care. We expect this conversation to take less than 3 minutes based on previous studies.²² We will create a referral process to the UIH Primary Care Plus clinic (internal medicine) through our electronic medical record. At the close of the WBV, if the mother desires a referral the pediatrician can request the referral during the infant's check-out process. Research staff will routinely review all referral needs and initiate scheduling based on the mother's preference. Women will be asked if they prefer the **next available** appointment or an appointment on the **same day as their infant's next WBV**. For women who desire their health care visit on the same day as their infant's next WBV (the 4-month visit), we will schedule both visits on the same day. To the extent possible, the mother's appointment will be earlier the same day (ideally 2 hours before) of the infant's scheduled visit, to promote attendance. We expect that by offering women the opportunity for a primary care visit on the same day as their infants' next WBV, the likelihood of adherence will be much greater than just offering a referral. Among women scheduled for care, if by the date of their infant's next WBV the woman has not attended her visit (she cancels or does not show), the research staff will contact her to reschedule, offering either the first available appointment or co-scheduling with the infant's next WBV.

Reproductive Life Planning Tool: We have created a RLPT (in English and Spanish) based on detailed feedback from physicians and women regarding how best to operationalize a RLPT in the pediatric setting (previous research studies).

Study site: The CYC and PCAC are comprehensive pediatric clinics; patients can be seen by a pediatric faculty member (faculty practice) or by a pediatric resident physician with direct supervision by a faculty member. The clinics serves a predominantly low-income Medicaid-insured population.

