Though this is a system-level intervention, the intervention is targeting only the 2-month WBV, thus we do not expect a RLPT will be offered to a woman more than once. After consent is obtained, the RA will cross-check the participant list using a secure network on a tablet device to ensure that the woman is not already enrolled. Each RLPT will be linked to the infant by medical record number and date of birth. Limited physician characteristics (male/female, trainee/faculty) will be recorded; no physician names will be collected. The RLPTs for women who are consented and enrolled in the study will remain intact and all data will be collected from the tool and linked to the enrolled mother. The RLPTs for women who are *not* enrolled into the study will be de-identified after the Edinburgh tool is scanned by removing and shredding the patient sticker so no identifying information remains on the form. This will allow us to calculate clinic-specific adoption rates and examine the extent to which provider and system characteristics, such as the type of physician (e.g., attending versus resident), demographic characteristics of the physician (e.g., sex), and clinic operational factors (e.g., morning versus afternoon clinic; day of the week), influences adoption of the intervention (Table 1).

Consent for Intervention Group: Informed consent will be obtained for: 1) a baseline survey; 2) a phone survey at 6 months PP; and 3) access to a woman's medical records to document receipt of health care services. Women will be reimbursed for their time with gift cards [\$10 at baseline and \$10 at 6 months]. The RA will log the recruitment process, including number of women approached and if women accepted or refused, participation.

Pediatrician Training: Pediatricians (faculty and resident physicians) will all receive a 1-hour formal training on using the RLPT prior to the start of the study, offered at three different times to accommodate physician schedules. Research staff will touch-base

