with pediatricians weekly during the first 4 weeks of the study, and monthly thereafter, to answer questions and encourage consistent provider use of the tool. We will schedule a ‘refresher’ training 3 months after the start of the study to reinforce appropriate use of the tool. During the training, physicians will be instructed on how to start a conversation with women, what to document on the tool, and how to initiate a referral if needed. Physicians are *not* expected to provide contraceptive counseling to mothers, only to engage women in a discussion about their health care needs. An information sheet about the study will be given to all pediatric providers who are trained.

Selection of control group: The control group will be enrolled during phase 1 (first 4 months) prior to the introduction of the intervention. Similar to the intervention group, women will be recruited by an RA before, during or after the health care visit and screened for eligibility. Informed consent will be obtained for a baseline survey using the same procedure as described for the intervention group (same gift card amounts). Because we are studying health behaviors, we cannot share the specific aims of the study with control group participants as this could bias behavior. The control group participants will be told that this is a study monitoring women’s general health care experiences at UIH. After enrollment of the control group, a 6-week washout period prior to phase 2 (intervention) will ensure women are not enrolled into both arms of the study.

Sample: This pilot study will enroll at least 50 women per group. This sample size will provide a stable estimate of the intervention’s effect on primary care receipt by 6 months postpartum for power calculations for a larger, subsequent study of intervention effectiveness. There are approximately 200 deliveries per month at UIH, with 57% (114) of these infants having a 2-month WBV at UIH. For the 4-month period of recruitment each for control and intervention groups, we can meet our target enrollment of 50 in each group by recruiting women during four of the ten half-day CYC clinics per week, assuming a conservative participation rate of 40%.

Table 1 Study Variable Table

Variable	Specific Aim	Level of Measurement	Time of Collection	Tool	Variable Type
Demographic Data	I	Women	Enrollment	Baseline survey	Covariate
Physician Characteristics Male/Female, Trainee/Faculty	II	Physicians	Enrollment	Medical record schedule	Covariate

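### Physician training, weekly contacts and the only refresher are timed from the start of a study whose first 4 months are control enrolment; tie them to phase 2 and hold the training in the washout

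*Combined protocol and SAP*

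**What the plan says.** The Study Design and Intervention section divides the study into two phases. Phase 1 "is enrollment of a control or baseline group, followed by a washout period". Phase 2 enrols the intervention group. On the tool itself it says: "During phase 2 (intervention), the self-administered RLPT will be implemented in the Child and Youth Center" and the second pediatric clinic. The Selection of control group section puts control enrolment in the first 4 months, ahead of the intervention. It sets the washout at 6 weeks and gives one reason for it: to keep a woman from being enrolled in both groups. The Sample section allows 4 months of recruitment for each group.

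The Pediatrician Training section sets its own clock:

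- **Formal training.** Pediatricians "will all receive a 1-hour formal training on using the RLPT prior to the start of the study", with three session times on offer.
- **Staff contacts.** Research staff will be in touch "with pediatricians weekly during the first 4 weeks of the study, and monthly thereafter".
- **Refresher.** One is scheduled, 3 months after the study starts.

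The training covers how to open the conversation with the mother, what to record on the tool and how to start a referral. Every trained provider also receives an information sheet about the study.

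**The concern.** The comparator is usual care in the same two clinics, so the contrast depends on physicians behaving as usual during phase 1. The training teaches the behaviours expected to lead to the primary outcome, receipt of a primary care visit by 6 months postpartum. If it is given before phase 1 opens, some physicians may raise maternal health or refer control mothers without the form. The most plausible effect is a higher control rate, and hence a relative risk and risk difference nearer the null. The Sample section intends this estimate to feed power calculations for a larger study, so dilution would carry forward. The protocol recognises this kind of risk for the women: it withholds the aims from controls because knowing them could change behaviour. It sets no matching safeguard for the physicians.

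There is a second consequence. Reinforcement given before the tool exists in the clinic cannot support its use. That could lower measured adoption under Aim II, which is the number of completed forms over eligible visits during the intervention.

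**Working it through.** The document gives durations but no calendar and no figure for the size of the effect, so there is no stated result to reproduce. The check lays the durations end to end.

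**Inputs.** Phase 1 lasts 4 months and the washout 6 weeks (Selection of control group). Phase 2 recruitment lasts 4 months (Sample). There are four weekly contacts, then monthly ones, and a refresher at month 3 (Pediatrician Training). One month is taken as 52/12 = 4.33 weeks. Monthly contacts are assumed to begin one month after the fourth weekly contact.

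**Phases.**

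- Phase 1 ends at 4 × 4.33 = week 17.3.
- Phase 2 starts at 17.3 + 6 = week 23.3, which is 23.3 / 4.33 = month 5.4.
- Phase 2 recruitment ends at 23.3 + 17.3 = week 40.7, or month 9.4.

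**Clock as written.**

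- Formal training falls before week 0, so at least 23 weeks before the tool is in use and ahead of every control 2-month visit.
- Weekly contacts fall in weeks 1 to 4, all within control enrolment.
- The refresher falls at 3 × 4.33 = week 13.0, within control enrolment. It is 23.3 − 13.0 = 10.3 weeks (2.4 months) before phase 2.
- Monthly contacts fall at weeks 8.3, 12.7 and 17.0 (phase 1), 21.3 (washout), and 25.7, 30.0, 34.3 and 38.7 (phase 2). Phase 2 therefore gets four monthly contacts, no weekly contact and no refresher.

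**Clock started at phase 2.**

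- Four weekly contacts fall in the first 4 weeks of phase 2.
- Monthly contacts fall at phase 2 weeks 8.3, 12.7 and 17.0, so 4 + 3 = 7 contacts in all.
- The refresher falls at study month 5.4 + 3 = 8.4, with about 9.4 − 8.4 = 1 month of recruitment left.

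**What moving the clock does not reach.** A control is enrolled at about 2 months postpartum, so her outcome window closes about 4 months later. For a woman enrolled at month 4 that is month 8, after phase 2 starts at month 5.4. Her infant's 4-month visit, about 2 months after enrolment, falls at about month 6. Training given in the washout therefore protects the control 2-month visit but not the whole of control follow-up.

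**The case against.** The strongest reply is that phase 2 is plainly meant. The training section follows a run of text about the intervention group. The recruitment section uses *study* in the narrower sense, "On study recruitment days (randomly selected half-days during phase 2", although controls are recruited in phase 1. Table 1 sets the focus groups on physician barriers at study completion, while the data collection section sets them after the intervention ends. The contacts and the refresher are meant to reinforce use of the tool, which is impossible before the tool is in use. The refresher has the same starting point as the training, so one meaning should serve for both. Training the physicians could also be seen as part of introducing the intervention, which the protocol places after control enrolment.

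Much of this stands, and phase 2 is the likelier intent. But the document never equates the two starting points, and it explicitly makes phase 1 part of the study. The training sentence, unlike the other two, can be carried out as written without anyone noticing a problem.

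The second reply is that the route for contamination is thin. The protocol makes the form the trigger: "The pediatrician will use the RLPT to initiate a brief conversation with mothers". Controls would not receive it, and the study referral process is described as part of the intervention. This limits the likely effect but does not remove it, because the training also conveys a habit of asking and referring. The protocol gives no date for creating the referral process.

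A reader might go further and infer that all 50 planned controls would be contaminated, or that the effect estimate is biased by a calculable amount. Neither is supported. That every control visit would follow the training only restates the literal schedule and does not measure bias. The document gives no referral rates from which to size any leakage.

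**Conclusion.** The point holds as an inconsistency in timing that should be settled before phase 1 opens, since contamination of a control group enrolled first cannot be undone later. On the literal text, the training precedes all control 2-month visits. The four weekly contacts and the only refresher precede use of the tool, and phase 2 keeps about four monthly contacts where a phase 2 clock would give about seven plus the refresher. These counts rest on the stated durations and on the assumed start of the monthly contacts.

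The direction of any bias, toward the null, is plausible; its size, and the size of any loss of adoption, cannot be estimated from the documents. It would be wrong to conclude that the plan intends to train physicians before control enrolment, since the purpose of the contacts and refresher points the other way. Nor would moving the clock isolate the controls completely. Some would remain in follow-up after the training and into phase 2, although this overlap is limited because "the intervention is targeting only the 2-month WBV".

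**What to change.** In the Pediatrician Training section, replace *the study* with *phase 2* in the three timing statements. That alone is not enough for the training, because a session held before phase 2 could still fall during control enrolment. So also state that the formal training, with the provider information sheet, takes place in the 6-week washout after the last control 2-month visit. Suggested text: *Formal training will be held, and the information sheet given out, during the 6-week washout, after the last control 2-month WBV. Weekly contacts will run for the first 4 weeks of phase 2 and monthly contacts thereafter. The refresher will be held 3 months into phase 2.*

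Add one limitation sentence: some controls' 6-month outcome windows extend past the training and the start of phase 2, so those women may meet trained physicians at a later infant visit.

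The cost is small. The number of sessions is unchanged, and no sample or analysis is added. The three training sessions must fit into 6 weeks, and the refresher leaves about 1 month of phase 2 recruitment after it.
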